### **D. Secondary Hypotheses**

Many neonates acquire *S. aureus* in the NICU from their parents

Treating *S. aureus* colonized parents of neonates requiring NICU care with intranasal mupirocin and topical chlorhexidine bathing will reduce neonatal *S. aureus* infections.

Treating *S. aureus* colonized parents of neonates requiring NICU care with intranasal mupirocin and topical chlorhexidine bathing will reduce parental *S. aureus* colonization.

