## 6. Allocation

**Randomization and masking:** This study has taken into consideration the guidelines for reporting of clinical trials as recommended by the CONSORT report to inform the study design. After recruitment and informed consent, parents will undergo pre-randomization screening. If both parents screen negative for *S. aureus* colonization, the neonate will be ineligible for the randomization and parents will be informed that they are not colonized at that time with *S. aureus*. If either parent screens positive for *S. aureus*, then both parents as a pair will be eligible for randomization to one of the two possible masked treatment arms. The neonate-parent "pair" will be the unit of randomization and each parent will be allocated to the same group if both consent. Because couples can re-expose each other after treatment (especially in households) we have chosen to treat both parents even if only one parent is colonized with *S. aureus*. To prevent potential feelings of guilt or one parent blaming another if only one parent is colonized, the parents will be told that one or both is colonized with *S. aureus* and they are eligible for randomization. Discordant parents will not be informed which is colonized and which is not colonized as we will treat both regardless.

Arm 1 will include assignment to masked intranasal mupirocin plus chlorhexidine gluconate cloths for topical antisepsis. Arm 2 will include assignment to masked placebo ointment and placebo cloths for skin antisepsis. Stratified permuted-block randomization will be performed using R statistical software to achieve balanced allocation of subjects within study site (Johns Hopkins Hospital vs. Bayview) and within strata of birth weight

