## D. Follow-up

**Parent Evaluation Time Points:** After randomization, the study team will provide the study drugs, study drug application instruction sheets and informational material. All participants will begin the 5-day treatment course at that time. During the 5-day treatment period, a study team member will contact the study participant daily at the bedside, on the phone, by email or by text message to assess compliance with treatment and to answer any questions. When available, parent(s) will be re-tested for colonization at 2-week intervals from randomization for the first 8 weeks and then every four weeks until discharge. Follow up swabs may be taken within a week of scheduled time points, based on participant availability. Anatomic sites to be tested and frequency of testing are detailed in Table 1. Peri-anal swabs will only be collected at enrollment and final screening. The final visit and testing will be performed at the time of a neonate's discharge from the NICU or at the time the child is identified to have acquired *S. aureus*.

**Neonate Evaluation Time Points:** After informed consent and randomization of parents, the neonate will undergo baseline testing to determine baseline *S. aureus* colonization status. This testing will occur on study day 1, the same day that parents begin treatment. Screening cultures will be performed by obtaining a swab from the following anatomical sites: anterior nares, the umbilicus, groin, and peri-anal area. If the nares site is not available to swab, the throat will be swabbed instead. Those neonates who test positive for *S. aureus* colonization at time of randomization will not be included in the primary analysis. After baseline testing, repeat testing will be performed every 7 days. Study samples will be saved and processed in the lab. The final visit and testing will be performed at the time of a neonate's discharge from the NICU.

Table 1

Frequency of Parent Swab Collection			
Site	Screening	Weeks 2, 4, 6, 8, 12, 16, 20, 24, 28,....	Time Neonate Acquires S. aureus
Nares	X	X	X
Throat	X	X	X
Groin	X	X	X
Peri-anal	X		X

Table 2

Frequency of Neonate Swab Collection			
Site	Parent Randomization	Weeks 1, 2, 3, 4,....	NICU Discharge
Nares	X	X	X
Umbilicus	X*	X*	X*
Groin	X	X	X
Peri-anal	X	X	X

\*Umbilicus will only be tested if the neonate has attached umbilical cord.

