Adverse events, as defined in Section 8, will be reported overall and separately by treatment group. Comparisons across treatment groups will be made using Fisher's Exact tests.

In addition, a series of planned secondary analyses will be conducted including subgroup analyses for the primary outcome, baseline-covariate adjusted analyses for the primary and secondary outcomes, per-protocol (PP) analyses for the primary and secondary outcomes and evaluation of patterns of loss and reacquisition of *S. aureus* among the parents (both treated and control).

Planned subgroup analyses include repeating the analysis for the primary outcome within strata defined by i) neonates with MRSA vs. those with MSSA, ii) collection site of colonization for the parent/caregivers, categorized as nares alone (i.e. all cultured parent/caregivers colonized in the nares) vs. nares + other (i.e. at least one parent/caregiver colonized in the nares) vs. non-nares; iii) LGA (large for gestational age) vs. SGA (small for gestational age); and iv) birthweight (< 1500g vs.  $\geq 1500$ g). The subgroup analyses will be based on Cox proportional hazards models that include a main term for treatment, a main term for subgroup (binary indicator) and the interaction between treatment and subgroup. Confidence intervals and the hypothesis test for no interaction will be derived based on the bootstrap procedure defined above.

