We will conduct a per protocol (PP) analysis. Compliance to treatment will be defined first for the individual parent and then for the family or parent/neonate dyad (Table 4). Individual parents will be classified as: confirmed compliant where the parent returns a treatment kit with ointment tubes with a broken seal; reported compliant where the parent gave responses to questions about feasibility and potential adverse effects (see Section 4.B compliance monitoring); and non-compliant where a) kits were returned unused, b) the parent reported non-use, or c) parent was lost to follow up without reporting use. We will define *compliance to treatment* for the individual parent as confirmed compliant, with a sensitivity analysis including reported compliant in the definition of *compliance to treatment*. Family compliance will be defined as both parents satisfying the *compliance to treatment* definition, with a sensitivity analysis where we include partially compliant families, i.e. if the parent identified to be colonized with *S. aureus* is compliant based on the individual parent definition and the non-colonized parent is non-compliant. Baseline characteristics of the parents, including age, race, education level, and recent antibiotic use, will be compared across the individual parent compliance definitions, overall and separately by treatment group. Baseline characteristics of the ITT and PP neonates will be compared, overall and separately for each treatment group. The analysis of the primary and secondary outcomes described above will be repeated among the subset of parent/neonate dyads who are observed to be compliant. Note, that we will assume that all placebo group patients are compliant. We will conduct the PP subset analysis using this assumption and then separately incorporating the compliance definitions above to the placebo group as well. Conditioning on compliance, a post-randomization variable, may introduce bias into any treatment comparisons. Therefore, we will also implement a causal inference approach using available baseline parent and neonate variables within an inverse probability weighted approach to estimate the treatment effect for the primary and secondary outcomes, where the treatment effect compares what would have happened if all patients receiving the treatment were compliant vs. if all patients receiving the placebo were compliant.

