**Table 4: Definition of individual parent and family compliance to treatment**

Individual parent compliance assessment		
Category	Sub-category	Definition
Compliant	Confirmed compliant	seal broken on nasal ointment
	Reported compliant	participants reported use
Non-compliant	Confirmed non-compliant	kits were returned unused
	Reported non-compliant	parent reported non-use
	Presumed non-compliant	parent was lost to follow up without reporting use
Family- level compliance assessment		
Category	Individual 1 compliance	Individual 2 compliance
Compliant	Compliant	Compliant
Partially compliant +	Compliant (SA colonized)	Non-compliant (not SA colonized)
Non-compliant	Compliant (not SA colonized)	Non-compliant (SA colonized)
Non-compliant	Non-compliant	Non-compliant

+partially compliant if *S. aureus* colonized parent is compliant, even if the non-colonized parent was non-compliant

Lastly, within each treatment group, we will use standard survival analysis methods (e.g. Kaplan-Meier survival function curve) to explore the loss of and potential reacquisition of *S. aureus* among the parents, separately for each treatment group. Cox proportional hazards models will be used to describe the association between loss of and reacquisition of *S. aureus* with baseline parent characteristics and treatment.

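### The planned treatment hazard ratio for parental reacquisition is not a randomized comparison, because only parents who have first lost S. aureus can reacquire it

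*Combined protocol and SAP*

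**What the plan says.** The Secondary Hypotheses (Section 3.D) include that mupirocin and "topical chlorhexidine bathing will reduce parental *S. aureus* colonization". Eradication of parental colonization is secondary outcome 3 in Section 5.B. The analysis is in the last paragraph of Section 9.C, after Table 4. Kaplan-Meier methods will be used "to explore the loss of and potential reacquisition of *S. aureus* among the parents, separately for each treatment group", and Cox models will then describe "the association between loss of and reacquisition of *S. aureus* with baseline parent characteristics and treatment". The same section lists this work among the planned secondary analyses.

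The plan does not define loss, the time origin or the risk set for reacquisition. Under Section 4.D, parents are, when available, "re-tested for colonization at 2-week intervals from randomization for the first 8 weeks and then every four weeks until discharge". The final parent visit is at the neonate's NICU discharge or when the neonate acquires *S. aureus*. Peri-anal swabs are taken only at enrollment and at the final screening.

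For the per-protocol analysis, Section 9.C warns: "Conditioning on compliance, a post-randomization variable, may introduce bias into any treatment comparisons". It adds an inverse-probability-weighted analysis there. Nothing similar is written for reacquisition.

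**The concern.** Being at risk of reacquisition depends on an event after randomization that treatment is meant to cause. In the active arm, parents become negative mainly because they were treated. In the placebo arm they become negative because their carriage was short-lived, or because a swab missed it. Randomization does not balance these two groups. Adjusting for baseline parent characteristics helps only as far as those characteristics capture carrier type, and none of the parent items listed in Section 8 measures it directly.

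Two mechanisms push in opposite directions:

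- **Carrier mix.** If persistent carriers rarely clear on their own but recolonize quickly once cleared, treatment brings more of them into the risk set. The ratio is pushed above 1.
- **Missed carriage.** A carrier with one false-negative visit appears to lose and then regain *S. aureus*. Such parents form a larger share of the placebo risk set, which pushes the ratio below 1. Omitting the peri-anal site at interval visits could add to this.

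At stake is how the trial describes the durability of decolonization, which helps to explain the neonatal result. A ratio produced by selection could be read as treatment protecting against recolonization, or as promoting it.

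**Working it through.** The plan gives no figure for parental loss or reacquisition, so there is none to reproduce. Every rate below is an assumption, and the true effect of treatment on reacquisition is set to nil throughout.

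**Carrier mix, perfect swabs.** Assume 60% persistent and 40% transient carriers. Treatment clears 85% of both types by the first visit. Placebo loss per visit is 5% (persistent) and 40% (transient). Reacquisition per visit is 30% and 10% in both arms. For parents first negative at week 2:

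- Active: the mix stays 60/40, so the risk at the next visit is 0.60 × 0.30 + 0.40 × 0.10 = 0.220.
- Placebo: losses are 0.60 × 0.05 = 0.03 persistent and 0.40 × 0.40 = 0.16 transient. The persistent share is 0.03/0.19 = 0.158, and the risk is 0.158 × 0.30 + 0.842 × 0.10 = 0.132.
- Ratio: 0.220/0.132 = 1.67.

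Over four two-weekly visits, counting time from each parent's first negative visit and pooling over intervals (Mantel-Haenszel), the ratio is 1.55.

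**Missed carriage, no carrier heterogeneity.** Assume spontaneous loss of 5% per visit and reacquisition of 15% per visit for everyone, 85% cleared by treatment, and 85% swab sensitivity. A missed carrier is positive at the next visit with probability 0.95 × 0.85 = 0.8075. A true loser is positive with probability 0.15 × 0.85 = 0.1275.

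- Placebo: 0.05 are truly negative and 0.95 × 0.15 = 0.1425 are missed, so 0.1425/0.1925 = 74% of apparent losers still carry. Risk: 0.740 × 0.8075 + 0.260 × 0.1275 = 0.631.
- Active: 0.85 are truly negative and 0.15 × 0.15 = 0.0225 are missed, so 0.0225/0.8725 = 2.6% still carry. Risk: 0.026 × 0.8075 + 0.974 × 0.1275 = 0.145.
- Ratio: 0.145/0.631 = 0.23 in the first interval. Pooled over four visits it is 0.31.

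**Both mechanisms, and other rates (pooled ratios, same four-visit set-up):**

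| Placebo loss per visit | Reacquisition per visit | Sensitivity | Spurious ratio |
|---|---|---|---|
| 5% / 40% | 30% / 10% | 100% | 1.55 |
| 5% / 40% | 30% / 10% | 95% | 1.02 |
| 5% / 40% | 30% / 10% | 90% | 0.83 |
| 5% / 40% | 15% for all | 95% | 0.70 |
| 5% / 40% | 15% for all | 85% | 0.53 |
| 5% for all | 15% for all | 95% | 0.40 |
| 5% for all | 15% for all | 85% | 0.31 |

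**Second set-up, with a fitted Cox model.** Parents are swabbed at weeks 2 to 24 on the plan's schedule, mean follow-up is 8 weeks, half are persistent carriers, and treatment clears 80% (up to 90% of transient carriers in the two strongest cases).

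- Perfect swabs: 1.00 with no heterogeneity, 1.18 mild, 1.41 moderate, 1.76 strong, 2.57 very strong.
- No heterogeneity: 0.66 at 90% sensitivity and 0.58 at 80%. With low turnover and 85% sensitivity it is 0.27.
- Moderate heterogeneity: 0.86 at 90% sensitivity and 0.71 at 80%.
- Perfect swabs, adjusting for the normally unobserved carrier type: 0.99 to 1.05. With perfect swabs the departure therefore comes from who enters the risk set.

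**The case against.** The strongest reply is that the analysis is secondary and worded as exploring and describing. It claims no causal effect and cannot affect the primary result. That limits the severity. It does not stop a hazard ratio for treatment in a randomized trial being read as a treatment effect, and the within-arm curves already serve description.

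A second reply is that the plan fixes no risk set, so conditioning on loss is an inference. This is fair as to the text, but the alternatives do not rescue the ratio. A multistate model's hazard from negative to positive is still conditional on being negative. Counting from randomization in all screening-positive parents would restore randomization, but a placebo parent who never cleared would then count as free of reacquisition. That is not durability.

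A reader might infer that no planned analysis gives a randomized answer on parental colonization. The documents do not support that. The Cox model for loss, in the same sentence, is a randomized comparison of first loss if limited to parents positive at screening, a status fixed before randomization. What it leaves open is whether clearance lasts.

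A reader might also take prevalence at each visit as wholly free of bias. It avoids conditioning on loss. However, re-testing depends on availability and stops at discharge or neonatal acquisition, and treatment is meant to change the latter. Later visits therefore also condition on remaining in follow-up.

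**Conclusion.** The concern stands in a limited form. If reacquisition is modelled after loss, as the word implies, the treatment hazard ratio compares groups selected after randomization. It can depart from 1 in either direction with no treatment effect on reacquisition.

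A reader might infer that the ratio will be far from 1, or that its sign can be predicted. Neither follows. Under the assumed rates it runs from about 0.3 through about 1.0 to 1.5 or more, and the two mechanisms can cancel (1.02 in one case above). The documents give no carriage, clearance, reacquisition or swab-sensitivity rates to narrow this. The plan recognises the same kind of bias for compliance, so extending that caution here fits its own reasoning. The issue is worth correcting before the database is locked, but it is confined to a secondary, descriptive analysis.

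**What to change.** In the last paragraph of Section 9.C:

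1. Define loss, and remove treatment as a covariate from the reacquisition Cox model. Keep the within-arm reacquisition curves, labelled as descriptive and not a treatment effect.
2. State that the loss model is limited to parents positive at screening, with time zero at randomization. This matters because partners negative at screening are also treated.
3. For durability, compare the arms among all parents positive at screening on the proportion colonized at weeks 2, 4, 6 and 8. Use the nares, throat and groin swabs taken at every visit, with intervals from the family-level bootstrap already planned.
4. Report by arm the number tested at each visit and the reasons for missing or ended follow-up: unavailable, discharge, or neonatal acquisition.

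The cost is a change of wording, one additional table and the loss of a treatment ratio for reacquisition. No new data are needed.

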## **10. Payment and Remuneration**

Each study participant will receive gift cards worth \$10 dollars at screening, when each kit is returned, if the participant completed treatment, and at Week 4, or at the final surveillance screening, whichever occurs first, up to a maximum of \$30 total.

## **11. Costs**

There are no direct costs to the patient in this study. All study related supplies will be provided.

